13.6.2. Sensitivity Analysis

The primary analysis will be repeated in the PP and the uMGMT stratum.

The primary analysis will also be repeated taking all received HRQoL forms into account (ie, including invalid/unassigned forms). In addition, two new summary statistics will be created:

- Deterioration during treatment (D10-DT) = A binary variable indicating whether the subject experienced a 10-point decrease from baseline at any post-baseline visit up to and including the end of study treatment visit.
- Deterioration after treatment (D10-AT) = A binary variable indicating whether the subject experienced a 10-point decrease from baseline at any follow-up visit (ie, after the end of study treatment visit).

Description of the D10-DT and D10-AT will be presented (mean, standard deviation, median, first and third quartiles, minimum, maximum) by treatment group together with mean difference, 95% CI to supplement the main analysis.

13.6.3. Missing Data

Missing data are a potential major source of bias in HRQoL assessment. In order to check the potential impact in the study, the compliance mechanism will be investigated prior to initiating the HRQoL analysis. Characteristics of subjects with and without valid HRQoL data will be compared and trends over time per dropout pattern will be investigated. Model building will be used in order to investigate whether the compliance mechanism is linked to selected prognostic variables.

Once the main analysis is completed, sensitivity analyses will be undertaken if warranted by the proportion and pattern of missing data to verify the robustness of the results related to the missing data. The sensitivity analysis will not be performed if the proportion of missing data is < 20%.

In case overall compliance is deemed too low (< 70%), only an exploratory analysis will be performed instead of the main analysis.

14. References

- Bretz F, M. W. (2009). A graphical approach to sequentially rejective multiple test procedures. *Stat Med*, 28(4):586-604.
- Brown PD, B. J. (2003). Effects of radiotherapy on cognitive function in subjects with low grade glioma measured by the Folstein Mini-Mental State Examination. *J Clin Oncol*, 21(13): 2519-24.
- Chinot OL, W. W. (2014). Bevacizumab plus radiotherapy-temozolomide for newly diagnosed glioblastoma. *N Engl J Med*, 370(8): 709-22.
- Cocks K, K. M.-J. (2012). Evidence-based guidelines for interpreting change scores for the European Organisation for the Research and Treatment of Cancer Quality of Life Questionnaire Core 30. *Eur J Cancer*, Jul;48(11):1713-21.
- Folstein MF, F. S. (1975). Mini-mental state: A practical method for grading the cognitive state of subjects for the clinician. *J Psychiatr Res*, 12(3): 189-98.
- Gilbert MR, D. J. (2014). A randomized trial of bevacizumab for newly diagnosed glioblastoma. *N Engl J Med*, 370(8): 699-708.
- Lin D., W. L. (1993). Checking the Cox Model with Cumulative Sums of Martingale-Based Residuals. *Biometrika*, 80, 557–572.
- Maringwa J, Q. C.-V. (2011). Minimal clinically meaningful differences for the EORTC QLQ-C30 and EORTC QLQ-BN20 scales in brain cancer patients. *Ann Oncol*, Sep;22(9):2107-12.
- Tagalos EG, S. G. (1996). The Mini-Mental State Examination in general medical practice: clinical utility and acceptance. *Mayo Clin Proc*, 71: 829-37.

15.1. Handling of Dates

Dates will be stored as numeric variables in the SAS analysis files and reported in DDMMYYYY format (i.e. the Date9. datetime format in SAS). Dates in the clinical database are classified into the categories of procedure dates, log dates, milestone dates, outcome dates, and special dates.

- Procedure Dates are the dates on which given protocol-specified procedure are performed. They include the dates of laboratory testing, physical examinations, tumor scans, etc. They should be present whenever data for a protocol-specified procedure are present and should only be missing when a procedure are marked as NOT DONE in the database. Procedure dates will not be imputed.
- Log Dates are dates recorded in CRF data logs. Specifically, they are the start and end dates for adverse events and concomitant medications/procedures. They should not be missing unless an event or medication is marked as ongoing in the database. Otherwise, incomplete log dates will be imputed according to the following rules (e.g. for duration or cycle assignment, etc.):
 - If the day component is missing from a date, an interpolated date will be generated with day = 1.
 - If the month component is missing from a date, an interpolated date will be generated with month = July.
 - If the day and month component are missing from a date, an interpolated date will be generated with day = 1 and month = July.
 - If the year component is missing from a date, no interpolated date will be generated and the date will remain unknown.
- Milestone Dates are dates of protocol milestones such as randomization, study drug start date, study drug termination date, study closure date, etc. They should not be missing if the milestone occurs for a subject. They will not be imputed.
- Outcome Dates are dates corresponding to study endpoints such as survival, progression, etc. In most cases they are derived either from a milestone (e.g. the survival date is derived from the death date), or a procedure date (e.g. the progression date is derived from the date of the tumor scan that was used to determine progression). They may be subject to endpoint-specific censoring rules if the outcome did not occur, but they are not otherwise subject to imputation.
- Special Dates cannot be classified in any of the above categories. They may be subject to variable-specific censoring and imputation rules.

Dates recorded in comment fields will not be imputed or reported in any specific format.

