12.1.1. Treatment-emergent adverse events (TEAEs)

Adverse events will be analyzed in terms of TEAEs which are defined as AEs occurring or worsening on or after the date of start of treatment and within 30 days after the last treatment administration. AEs present at baseline which resolve during treatment and occurred again (at any grade) are considered TEAEs. AEs present at baseline which did not resolve within 30 days of the last treatment or which resolved but did not occur again are excluded from TEAEs.

Unless otherwise specified, summary of TEAEs will be provided for the whole study time and per period, overall and per treatment arm.

An overall summary of TEAEs will be provided for:

- subjects with at least one TEAE;
- subjects with at least one TEAE related to any study drug;
- subjects with at least one treatment-emergent serious AE (SAE)
- subjects with at least one treatment-emergent serious AE (SAE) related to any study drug;
- subjects with at least one CTCAE Grade 3 or 4 TEAE;
- subjects with at least one CTCAE Grade 3 or 4 TEAE related to any study drug;
- subjects with at least one TEAE leading to death (Grade 5);
- subjects with at least one TEAE leading to death (Grade 5) related to any study drug;
- subjects with at least one TEAE leading to dose reduction;
- subjects with at least one TEAE leading to dose interruption;
- subjects with at least one TEAE leading to study drug withdrawal;

In addition, TEAEs will be summarized per SOC and per PT for the following:

- all TEAEs;
- TEAEs, occurring for more than 10% of subjects in any treatment group;
- TEAEs related to any study drug (TMZ, MRZ);
- CTCAE Grade 3 or 4 TEAE;
- CTCAE Grade 3 or 4 TEAE related to any study drug;
- TEAEs by age group, for the whole study time only;
- TEAEs by sex, for the whole study time only;
- TEAEs by race, for the whole study time only;
- Treatment-emergent serious AEs (SAEs);
- Treatment-emergent serious AEs (SAEs) related to any study drug;
- TEAEs leading to death;
- TEAEs related to any study drug leading to death;
- TEAEs leading to dose reduction;
- TEAEs leading to dose interruption;
- TEAEs leading to study drug withdrawal.

Subjects with multiple occurrences of the same event will be counted only once per subject for each summary. Results will be reported in descending order of overall subject frequency in the overall column (unless otherwise specified) by SOC and by PT within the SOC. For summaries

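### SAP 15.1 sets a missing AE start day to the 1st of the month with no first-dose floor, so some on-treatment events fail the TEAE date test in 12.1.1 (minor)

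*SAP*

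**What the plan says.** **Date rule (SAP 15.1).** AE dates are classed as log dates: "Specifically, they are the start and end dates for adverse events and concomitant medications/procedures". The plan expects them to be complete: "They should not be missing unless an event or medication is marked as ongoing in the database". Incomplete ones are imputed as follows.
- Day missing: "If the day component is missing from a date, an interpolated date will be generated with day = 1".
- Month missing: "If the month component is missing from a date, an interpolated date will be generated with month = July".
- Both missing: "If the day and month component are missing from a date, an interpolated date will be generated with day = 1", again with July as the month.

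The lead-in gives duration and cycle assignment as examples of use and ends with an etc. Neither 15.1 nor 15.1.1 compares the imputed date with first dose.

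**TEAE test (SAP 12.1.1).** TEAEs are "AEs occurring or worsening on or after the date of start of treatment", up to 30 days after the last administration. No partial-date rule is given here.

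**Where the classification is used.** It drives the TEAE tables in 12.1.1 and the treatment-emergent AESI tables in 12.1.3, for the whole study and by period. Under SAP section 12 the concomitant period starts at the first radiotherapy administration. It ends 27 days after the last one, or earlier if adjuvant TMZ starts.

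**Contrast.** For concomitant medications, SAP 9.4 does say how a record with a missing start or end date is classified. AEs have no equivalent.

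**The concern.** Moving a start date to the 1st of its month can only leave it unchanged or make it earlier. For an AE that began on treatment in the month of first dose, the 1st almost always lies before first dose. The event then fails a test it truly meets, and it also falls before the concomitant period opens. The 1 July rule does the same when first dose was after 1 July of the onset year.

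The events at risk are the earliest on-treatment onsets. The AESI categories (ataxia, dysarthria, hallucination/delirium) are in these tables, and the IDMC cited neurological and neuropsychiatric toxicity when it recommended stopping recruitment. SAP section 3 has the safety section reported in full at both the primary and the long-term follow-up analysis, so both carry the rule. A misdated event would not necessarily stand out, because Protocol 7.2.1 starts AE collection two weeks before randomization and a pre-dose AE date is therefore often valid.

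**Working it through.** The plan states no figure here to reproduce. The check applies the 15.1 rule and the 12.1.1 test to every possible date. Every result is conditional on a partial date.

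**Inputs.** Radiotherapy lasts 6 weeks (42 days), with a maximum overall time of 49 days (Protocol 5.7.4, 5.7.8). The concomitant period runs to 27 days after the last fraction (SAP 12). TMZ starts on the first day of radiotherapy (Protocol 5.1.2), so first dose and period start are taken as the same day. Assumptions: a 365-day year, with first-dose and onset dates uniform.

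**1. Example.** First dose is 12 March and true onset is 20 March, Study Day 20 − 12 + 1 = 9. With the day missing, the start becomes 1 March, Study Day 1 − 12 = −11. The event is not a TEAE.

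**2. Onset in the first-dose month.** In a month of L days, the pairs with onset on or after first dose number L(L+1)/2. All fail except those with first dose on the 1st, so L(L−1)/2 fail.

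| L | Fail / all | Share |
|---|---|---|
| 28 | 378/406 | 93.1% |
| 30 | 435/465 | 93.5% |
| 31 | 465/496 | 93.8% |

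Over the year, 7×465 + 4×435 + 378 = 5373 pairs fail, out of 7×496 + 4×465 + 406 = 5738 (93.6%). This is a share of date combinations, not of AEs.

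**3. Share of all missing-day onsets in a window of W days.** Share = 5373/(365 × W). Each W below exceeds 31 days, so the window contains every failing pair.
- W = 42 + 27 = 69: 5373/25185 = 21.3%
- W = 49 + 27 = 76: 5373/27740 = 19.4%
- W = 180: 5373/65700 = 8.2%
- W = 365: 5373/133225 = 4.0%

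**4. July rules, onset in the first-dose year.** There are 365×366/2 = 66795 pairs.
- Day and month missing: 1 July is day 182, so pairs fail when first dose is on day 183 or later. 183×184/2 = 16836, and 16836/66795 = 25.2%.
- Month only missing: 2325 pairs (first dose in July) + 11781 (August to December) = 14106, and 14106/66795 = 21.1%.

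**5. Effect of a first-dose floor.** None of the 5738 first-month pairs then fails. The floored start precedes the true onset by at most 29 days (mean 9.5), so it stays inside a 69-day concomitant period. Missing-month dates should not be floored in this way: 295×296/2 = 43660 of the 66795 same-year pairs (65.4%) have onset more than 69 days after first dose.

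**6. Exposure to the opposite error.** The baseline AE assessment is within 7 days of randomization (Protocol 6.1). Treatment starts within 1 week of randomization, with a 48-hour delivery allowance (Protocol 6.2). Onsets in up to 7 + 7 + 2 = 16 days can therefore escape the baseline check. For first-dose day d, min(d − 1, 16) of those days lie in the first-dose month. These sum to 360, 344 and 312 for months of 31, 30 and 28 days. 7×360 + 4×344 + 312 = 4208, and 4208/(365×16) = 4208/5840 = 72%.

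**The case against.** **Scope.** 15.1 does not name TEAE classification among its uses, so the rule might not be meant for it. That is possible, but the list is given only as examples, and no other rule tells a programmer what to do with a partial AE start date. The omission limits how firmly the defect can be stated; it does not remove it.

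**Frequency.** 15.1 expects complete dates. AEs are reviewed weekly during radiotherapy (Protocol 6.2.1), and consistency checks with queries are planned (Protocol 15.2). Whether the eCRF accepts a partial AE start date depends on guidelines that are not in these documents. "Subjects with multiple occurrences of the same event will be counted only once per subject for each summary", so one misdated record matters only if no other record puts the subject in the same cell. A misdated event may still appear among AEs before start of treatment (SAP 9.1). SAEs are reconciled with the pharmacovigilance database (Protocol 8.2.3.2). All of this stands, and it is why the point is minor.

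**Opposite errors.** The July rules can move a pre-dose onset to after first dose, and day = 1 can pull an onset beyond the 30-day window back into it. This also stands: the figures above count one kind of error and do not give a net effect.

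**Two stronger readings do not hold.** A reader might infer that 12.1.1 fails to handle a baseline AE that worsens, because "AEs present at baseline which did not resolve within 30 days of the last treatment or which resolved but did not occur again are excluded" carries no exception for a rise in grade. But the first sentence of 12.1.1 includes worsening, and Protocol 7.2.1 closes the initial record and opens a new one at each change in severity. The worsened grade therefore has its own on-treatment start. The SAP does not spell out this per-record convention, but that is missing detail, not a gap in the definition. A reader might also infer that the date rule hides early marizomib toxicity. The rule is the same in both arms, and the documents give no partial-date counts by arm.

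**Conclusion.** The point holds as a minor defect in a stated rule. SAP 15.1 has no first-dose floor and the SAP has no other partial-date rule for AEs. As written, an on-treatment AE with a missing start day in the month of first dose fails the 12.1.1 test unless dosing began on the 1st.

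Among missing-day onsets in the concomitant period, about 21% (69 days) or 19% (76 days) would be lost. These shares assume uniform dates and that 15.1 is applied to TEAE classification. They do not estimate the effect on any table, because the number of partial AE dates is unknown. The absolute effect is probably small, and the documents support no claim of bias between arms.

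**What to change.** Keep the 15.1 imputation rules and add:

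> For TEAE classification, if an AE start date is partial and its known parts are compatible with onset on or after first dose, the AE is treated as treatment-emergent, unless the known parts of its end date place it before first dose, the AE was recorded at the baseline AE assessment, or the known parts place onset more than 30 days after last treatment. For an AE that is treatment-emergent under this rule, if only the day is missing and the month is that of first dose, the start date is set to the first-dose date; other partial start dates are not moved, and such AEs with a missing month that are imputed before first dose count in whole-study summaries only.

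The end-date check must use known parts only, because an end date with a missing day is itself imputed to the 1st.

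**Cost.** A short SAP addition and minor programming. Some AEs that truly began before first dose may be counted as TEAEs. Onsets up to about 16 days before first dose can escape the baseline check, and about 72% of those with a missing day would fall in the first-dose month. AEs with a missing month that are imputed before first dose will be absent from the period tables.

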15.1.1. Calculation Using Dates

Calculations using dates (e.g., subject's age or relative day after the first dose of study drug) will adhere to the following conventions:

- Study days after the start day of study drug will be calculated as the difference between the date of interest and the first date of dosing of study drug plus 1 day. The generalized calculation algorithm for relative day is the following:
 - If TARGET DATE \geq DSTART then STUDY DAY = (TARGET DATE – DSTART) + 1;
 - Else use STUDY DAY = TARGET DATE – DSTART.

Note that Study Day 1 is the first day of treatment of study drug. Negative study days are reflective of observations obtained during the baseline/screening period. Note: Partial dates for the first study drug are not imputed in general. All effort should be made to avoid incomplete study drug start dates.

Subject's date of birth will not be collected in this trial. Age at registration, age at randomization (expressed in years) are extracted from study eCRFs.

15.2. Censoring Rules for PFS

Situation	Date of Progression or Censoring	Situation/Outcome
No baseline assessments and alive after 2 scheduled assessments	Randomization	Censored
Death within the first two scheduled assessments without any adequate assessment	Date of death	Event
Death between adequate assessments	Date of death	Event
No progression	Date of last adequate assessment with evidence of no progression	Censored
Study discontinuation for reasons other than disease progression or death	Date of last adequate assessment with evidence of no progression	Censored
New anti-cancer therapy or cancer-related surgery prior to progression or death	Date of last adequate assessment after start of new anti-cancer therapy or cancer-related surgery with evidence of progression prior	Event
	Date of last adequate assessment after start of new anti-cancer therapy or cancer-related surgery with evidence of no progression	Censored
Death or progression after an extended lost-to-follow-up time (two or more missed scheduled assessments)	Date of last adequate assessment with evidence of no progression	Censored

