Unless otherwise specified, the baseline observation is defined as the last non-missing measurement collected prior to or on randomization. If no measurement collected prior to or on randomization, then the last non-missing observation prior to or on the first dose date of study drug (TMZ/MRZ) is considered.

Definition of Final Observation

For lab and vital sign parameters, the final observation is defined as the last non-missing post-baseline measurement collected during the study.

Time-to-Event Endpoints

All time-to-event (TTE) endpoints are defined using a time variable and an event indicator. The time variable represents the time from a pre-defined time origin to the onset of a predefined event of interest or the last time when adequate assessments have been made to rule out the onset of the event. The latter case indicates that the endpoint has been right-censored. In this study, a time variable is defined as the date of event or censoring - date of randomization + 1. The event indicator is set to 0 if the event has been observed during the course of the study and 1 if it is censored. When multiple assessments are needed to ascertain the occurrence of an event, the earliest date among all of these assessments is taken to be date of the event or censoring. The time variable will be computed in days and converted into months (1 month = 30.4375 days) for analysis of TTE

endpoints. When no post-randomization observations are available for a subject for any given endpoint, then the endpoint is taken to be censored on the date of randomization. All TTE endpoints defined in this study are concerned with only the first incidence of an event of interest, and recurrence of the same event is not considered. An event, however, may be defined in a composite fashion, i.e. as the occurrence of one among several different outcomes. An example of such an endpoint is PFS where the event is either disease progression or death. The composite event is observed when at least one of the component events occurs, and the time to the earliest among the occurring component events is considered to be the TTE for the composite event.

End of Study

End of study occurs when all of the following criteria have been satisfied:

- 1. Thirty days after all subjects have stopped protocol treatment
- 2. The trial is mature for the analysis of the primary endpoint as defined in the protocol
- 3. The database has been fully cleaned and frozen for this analysis

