11.3.1. Progression-free Survival

Progression-free survival will be defined as the number of days from date of randomization to the date of earliest disease progression based on Response Assessment in Neuro-Oncology (RANO) criteria (as determined by the Investigator) or to the date of death due to any cause, if disease progression did not occur (the date of progression or death or censoring - date of randomization + 1). Subjects for whom neither death nor progression have been documented will be censored at the date of the last radiological assessment that the subject was progression-free. If a subject has no post-baseline radiological assessment, then the data will be censored at the date of randomization.

Subjects with two or more missing assessments prior to a visit with documented disease progression (or death) will be censored at the last assessment where the subject was documented to be progression free. Subjects who received new anti-cancer therapy or cancer-related surgery prior to progression or death will not be censored at the last assessment where the patient was documented as progression free prior to the new anti-cancer therapy or cancer-related surgery. Censoring rules are documented in section 15.2.

The following PFS analyses will be performed at 2-sided significance level $\alpha=0.05$ for exploratory purpose. The stratified LogRank test will be applied on the PFS time to test for differences between the 2 treatment groups. The Cox's proportional hazards model stratified by the stratification factors assessed at randomization (except institution) will provide the HR (including 95% CI). Summary of associated statistics for each treatment arm (median PFS time, 6-, 12-, 18-, 24-month PFS rate estimates and estimates for every 6 months thereafter as applicable) will be displayed with 95% CI computed using the same methods as for OS, and the Kaplan-Meier curve for PFS will be presented.

Progression-free survival Kaplan-Meier estimates will be calculated and unstratified Cox's proportional hazards model will be fitted for each subgroup defined in Section 11.5 in the ITT population only. Forest Plot will be displayed with a subgroup by treatment interaction test.

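### The new-therapy row of the SAP 15.2 PFS table dates progression at the last rather than the first progressing scan, and leaves a death after new therapy with two possible outcomes

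*SAP*

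**What the plan says.** SAP 11.3.1 measures PFS to "the date of earliest disease progression based on Response Assessment in Neuro-Oncology (RANO) criteria", "or to the date of death due to any cause, if disease progression did not occur". It says that new anti-cancer therapy or cancer-related surgery does not trigger censoring at the preceding progression-free assessment, and then states: "Censoring rules are documented in section 15.2". Protocol 7.1.3 gives the same definition and leaves detailed censoring to the SAP.

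SAP 6.1 sets the general rule for composite endpoints: "the time to the earliest among the occurring component events is considered to be the TTE for the composite event". The RANO text in SAP 11.3.2 adds that when equivocal progression is later confirmed, the earlier date counts.

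In SAP 15.2 the situation "New anti-cancer therapy or cancer-related surgery prior to progression or death" has two outcomes:

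- Event, dated "Date of last adequate assessment after start of new anti-cancer therapy or cancer-related surgery with evidence of progression prior".
- Censored, dated "Date of last adequate assessment after start of new anti-cancer therapy or cancer-related surgery with evidence of no progression".

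Elsewhere the same table makes death an event in two rows: death within the first two scheduled assessments without an adequate assessment, and death between adequate assessments. Its final row censors progression or death after two or more missed assessments. It has no row for ordinary documented progression.

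**The concern.** The body text and the table give different PFS dates for the same patient, and the body text sends the programmer to the table. Because there is no ordinary progression row, the new-therapy row is the only line in 15.2 that dates a progression event, and it says last where 11.3.1 and 6.1 say earliest.

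The row's heading mentions death but neither of its outcomes does. Two programmers working from 15.2 could give the same patient a different date, or a different event status. PFS is the only endpoint that the SAP lists as key secondary. Response duration (SAP 11.3.2) is measured in the same way as PFS and inherits the ambiguity. Both are due again in the long-term follow-up analysis.

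**Working it through.** The plan states no PFS sample size, event count or power, so there is no figure to reproduce. The check is a comparison of texts, followed by an illustration of size.

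**1. Progression after new therapy**

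| Source | Date used |
|---|---|
| SAP 11.3.1 | earliest RANO progression |
| SAP 6.1 | earliest component event |
| SAP 11.3.2 (equivocal, then confirmed) | earlier date |
| SAP 15.2, new-therapy row | last adequate assessment with progression |

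The 15.2 cell also ends in a stray word (prior), so something may be missing from it. Nothing in what remains turns last into first.

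**2. Death after new therapy, no documented progression**

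- SAP 11.3.1: event at death.
- SAP 15.2, row for death between adequate assessments: Event.
- SAP 15.2, new-therapy row: only the no-progression line fits, so Censored.
- If no scan followed the new therapy, the new-therapy row supplies no date, because both its lines need an assessment after therapy started. Protocol 5.3 allows imaging to stop at a new regimen, so this can happen.

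No order of precedence between rows is given.

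**3. Shift per affected event**

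Inputs: MRI every 8 weeks (protocol 6.2.2, 6.3.2.1); confirmation MRI 4 weeks later (SAP 11.3.2); 30.4375 days per month (SAP 6.1).

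- One progressing scan: 0.
- Confirmation scan taken as the last: 28 / 30.4375 = 0.92 months.
- k scheduled progressing scans: (k − 1) × 56 days. For k = 2, 56 / 30.4375 = 1.84 months (8 weeks). For k = 3, 112 / 30.4375 = 3.68 months (16 weeks).

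**4. Effect on the hazard ratio (inputs assumed)**

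Null simulation: exponential PFS in both arms, median 7 months (7 × 30.4375 / 7 = 30.4 weeks); first scan at week 10 (6 weeks of RT plus 4), then every 8 weeks; a share of each arm has its event delayed; Cox HR, marizomib over control.

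| Affected, control v marizomib | Delay 8 weeks | Delay 16 weeks |
|---|---|---|
| 10% v 5% | 1.01 | 1.02 |
| 15% v 5% | 1.02 | 1.04 |
| 10% v 10% | not run | 1.00 |

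This models delayed dates only, not censored deaths.

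**5. Effect on the Kaplan-Meier estimate (inputs assumed)**

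Same median and scan grid, one arm. Assumed: 10-30% of patients start new therapy first; 0-50% of those die without documented progression and are all read as Censored; 0-2 extra progressing scans.

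| Setting | 6-month PFS | 12-month PFS |
|---|---|---|
| Definition in 11.3.1 | about 55% | about 32% |
| One progressing scan, no such deaths | no change | no change |
| No date shift; 10% start new therapy, 25% of them die | 56.0% | 32.8% |
| No date shift; 30% start new therapy, 50% of them die | 59.9% | 37.4% |
| Upper end: 30%, 50%, two extra scans | 63.7% | 39.6% |

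**The case against.** The case for leaving this as a minor wording matter has several good parts.

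- **Repeat progressing scans are not scheduled.** Follow-up imaging runs until progression (protocol 6.3.2.1), and after treatment stops without progression it may end at a new regimen (protocol 5.3). First and last progressing scans will often be the same scan. This stands, and it is why the range of the shift starts at zero. Repeats are still foreseeable: a confirmation MRI is required for equivocal progression, and protocol 7.1.1.1 allows treatment to continue after T2/FLAIR progression.
- **Death is covered elsewhere.** A reader might infer that 15.2 has no outcome for death, or that these deaths are certain to be censored. Neither is supported. Two rows make death an event, and 11.3.1 does too. The defect is an unresolved conflict between rows. The missed-assessments rule would also properly censor some of these deaths, which narrows the gap further.
- **PFS is not lengthened for every affected patient.** Censoring a death at an earlier scan shortens that patient's own time. The upward pull on the Kaplan-Meier estimate comes from the lost event.
- **Bias between arms is not shown.** One might argue from planned duration: 18 marizomib cycles against 6 temozolomide cycles is 12 × 4 = 48 weeks. But that gap opens only after 6 + 4 + 24 = 34 weeks, later than the assumed median of 30.4 weeks. Control patients may continue temozolomide to 12 cycles, and other systemic anti-cancer agents before progression are not permitted during study treatment (protocol 5.6.3). If only events after week 34 can be affected, 10% v 5% gives an HR of 1.004 to 1.009.

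None of this removes the contradiction between 15.2 and 11.3.1.

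**Conclusion.** The point holds as an error in one table row. As written, SAP 15.2 contradicts the SAP's own PFS definition on the date of progression after new therapy, and it leaves the status of a death after new therapy undetermined.

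The shift per affected event is 0, 4 weeks, or 8 to 16 weeks for two or three scheduled progressing scans. A reader might infer 16 to 24 weeks for that number of scans, but at 8-week intervals this would need three or four. With assumed shares of 10% v 5% and delays of 8 to 16 weeks, the null HR is about 1.01 to 1.02; with equal shares it stays at 1.00. If such deaths are censored, the Kaplan-Meier PFS estimate rises by an amount that depends wholly on how many there are. The documents give neither the number affected nor any difference between arms.

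PFS is tested at an exploratory two-sided 5%, and the OS analysis is untouched. The row should be corrected because following it can produce a wrong date or status, not because a material bias has been shown.

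**What to change.** Amend SAP 15.2 in three places:

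1. **New-therapy row.** Event at the first adequate assessment that documents progression, or at death if no progression came before it, whether or not new anti-cancer therapy or surgery was given. If neither occurs, censor at the last adequate assessment without progression.
2. **New general row.** Documented progression: Event at the first progression date.
3. **Precedence.** State that the row for two or more missed assessments overrides the others. Without this, the rewritten row would conflict with 11.3.1.

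Apply the same rules to response duration. If PFS has already been derived for the primary analysis, check which reading the program used and list any patient whose date or status changes.

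The cost is one edited row, one added row and one sentence. No new data are needed, and the PFS definition does not change.
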